#### 12.2.3 Related & Unexpected SAEs – Expedited Reporting

All Related & Unexpected SAEs occurring within 30 days of an investigation (angiography, stress CMR, CTCA) must be reported by the clinical research team in the eCRF within one working day of the investigator becoming aware of the event.

For each Related & Unexpected SAE the following information will be collected:

- full details in medical terms with a diagnosis, if possible
- its duration (start and end dates if applicable)
- action taken
- outcome
- causality (i.e. relatedness to investigation), in the opinion of the investigator

Any follow-up information should be added to the same Related & Unexpected Serious Adverse Event eCRF as soon as it is available. Events will be followed up until the event has resolved or a final outcome has been reached. All Related & Unexpected SAEs will be reviewed by the Chief Investigator and subject to expedited reporting to the Sponsor ([contact]) within 1 working day and the main REC on behalf of the Chief Investigator within 15 days.

#### **12.2.5** Serious Adverse Events (SAEs) that Do Not Require Reporting

SAEs deemed to be unrelated to randomised investigation by the site PI (or delegated investigator) will not be reported.

#### 12.2.6 Non-serious adverse events

Adverse Events (AEs) occurring during this timeframe must be recorded, assessed, reported and analysed in accordance with the UK Policy Framework for Health and Social Care Research and the study protocol. All AEs must be assessed for seriousness using the definitions above. Non-serious adverse events do not need to be reported within the eCRF but should be recorded within the patient's medical records.

#### **12.3 RESPONSIBILITIES**

#### Principal Investigator/Authorised Individual

1) Checking for SAEs when patients attend for routine treatment/follow-up

- 2) Judgement in assessing:
  - Seriousness
    - Causality
    - Expectedness

3) To ensure all Related & Unexpected SAEs are recorded and entered to the eCRF within 24 hours of becoming aware and to provide further follow-up information as soon as available

4) To report Related & Unexpected SAEs to local committees in line with local arrangements.

#### Chief Investigator or delegate

1) Assign relatedness and expected nature of SAEs where it has not been possible to obtain local assessment 2) Expedited reporting of Related & Unexpected SAEs to the main REC and Sponsor within required timelines 3) Review all events assessed as Related & Unexpected in the opinion of the local investigator, within the required timelines. In the event of disagreement between the local assessment and the Chief Investigator, local assessment may be upgraded or downgraded by the Chief Investigator prior to reporting to the main REC.

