#### 12.2.2 Related SAEs – Reported within standard eCRF

Related SAEs (expected and unexpected) for the randomised investigation alone that occur within 30 days will be collected. Adverse Events that occur during the hospitalisation for the procedure will be recorded in the eCRF but will not reported in an expedited manner unless unexpected.

Data to inform the objectives (deaths or hospitalisations) will be recorded from medical records but not designated as SAEs for both study arms outside of the SAE reporting period.

The following SAEs are expected within the trial population and will be reported by the clinical research teams using in the eCRF including:

- Angiography complications
  - Vascular complications
  - Peri-procedural stroke
  - o Peri-procedural MI
  - Allergic contrast reaction
- Allergic contrast reaction to either CTCA or stress CMR

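### The Chief Investigator may downgrade a site's related-and-unexpected judgement before the ethics committee is told, with no duty to disclose the disagreement

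*Protocol*

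**What the plan says.** Section 12.3, under the heading for the Chief Investigator or delegate, sets a review task: "Review all events assessed as Related & Unexpected in the opinion of the local investigator". If the two disagree, "local assessment may be upgraded or downgraded by the Chief Investigator prior to reporting to the main REC".

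Section 12.2.3 sets the expedited route: "All Related & Unexpected SAEs will be reviewed by the Chief Investigator and subject to expedited reporting to the Sponsor" within one working day, and to "the main REC on behalf of the Chief Investigator within 15 days". Among the items collected for each such event is "causality (i.e. relatedness to investigation), in the opinion of the investigator".

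Section 12.3 also gives the site's Principal Investigator or authorised individual the judgement of seriousness, causality and expectedness. Section 12.1 sets a low bar for related: it is enough that a causal link is a reasonable possibility that cannot be excluded.

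**The concern.** Two sections answer the same question differently: which assessment decides whether the main REC receives an expedited report? Section 12.2.3 reads as though every event in the category goes forward, with the site's view of causality recorded. Section 12.3 lets one person move an event out of the category before the committee hears of it. The protocol does not say whose view prevails for reporting, does not ask for reasons or a second reviewer, and does not require both opinions to be sent.

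What is at stake is timely independent sight of possible harm from a randomised test. The power also lies with someone who is not independent of the trial. Section 20.1 makes the Chief Investigator responsible for the trial's design, management, reporting and promotion, and section 20.2 places that role on the group that interprets and publishes the results.

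**Working it through.** No arithmetic applies, because the point rests on no event rate, margin or sample size. The check is to follow one event through the text.

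1. **Site assessment.** A site sees an SAE within 30 days of the test, cannot rule out a causal link, and finds it inconsistent with the list of expected events. Under sections 12.1 and 12.3 the site calls it related and unexpected.
2. **Data entry.** The site's duty is "To ensure all Related & Unexpected SAEs are recorded and entered to the eCRF within 24 hours of becoming aware" (section 12.2.3 says one working day). The event is therefore in the trial data before the Chief Investigator's decision matters.
3. **Chief Investigator review.** The event qualifies because the site put it in the category. Under this review there is little left to upgrade, since the event is already in the category that triggers expedited reporting. The useful direction of change is down, to unrelated or to expected. A separate item in section 12.3 lets the Chief Investigator assign relatedness and expectedness where no local assessment could be obtained, but that is a different situation.
4. **No matching check upwards.** Section 12.2.5 states that "SAEs deemed to be unrelated to randomised investigation by the site PI (or delegated investigator) will not be reported". An event that a site under-calls does not reach this review, so the review corrects in one direction only.
5. **REC report.** If the event is downgraded, it no longer belongs to the category that section 12.2.3 sends to the main REC within 15 days. No sentence keeps the report alive or requires the disagreement to be disclosed.
6. **Sponsor report.** Section 12.3 times the downgrade relative to the main REC only. It gives no power to withhold the event from the Sponsor, but it does not say whether the Sponsor is told before or after a downgrade.
7. **Other routes.** The site reports related and unexpected SAEs to local committees (section 12.3). The Robertson Centre for Biostatistics prepares safety data annually, and the steering and data monitoring committees meet at least annually (sections 12.3 and 20.2). Apart from the local reports, these are yearly cycles set against a 15-day limit for the REC. The Centre's alerts to investigators are also tied to the related-and-unexpected label.

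The gap is therefore at steps 5 and 6: the expedited REC report, and the order of events for the Sponsor.

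**The case against.** The strongest reply is that the sections are compatible. The sentence in section 12.2.3 that requires expedited reporting itself includes Chief Investigator review, and it does not say that the site's opinion alone fixes the category. The phrase about the investigator's opinion describes a data item. Section 12.3 then says what the review may do, and requires it within the set timelines. This stands as far as it goes: the two sections are unreconciled and do not flatly contradict each other. It does not say what the REC is told after a disagreement.

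A reader might infer more: that the clause lets an arm-aware trial lead strip harms from the trial's data and bias the comparison of procedural complications. The documents do not support that, for these reasons.

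- The review reaches only related and unexpected events. Section 12.2.2 lists vascular complications, peri-procedural stroke, peri-procedural MI and allergic contrast reactions as expected, so the usual complications never enter it. The 1% serious complication rate for invasive angiography in section 5 therefore cannot be used to count the events exposed.
- "Related SAEs (expected and unexpected) for the randomised investigation alone that occur within 30 days will be collected", so a change from unexpected to expected removes nothing from collection.
- The exemption in section 12.2.5 turns on the site's judgement. An event under this review has already been called related by the site.
- Nothing lets the Chief Investigator delete or recode an eCRF entry, and section 16.3 requires an audit trail for data changes.
- No text says that the exploratory complications analysis (sections 13.3 and 15.5) uses the Chief Investigator's classification. That choice may properly be left to the statistical analysis plan.
- Open-label conduct adds little here. Judging relatedness to a test requires knowing the test, so the site is equally aware of the arm.

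**Conclusion.** The point holds in limited form. As written, section 12.3 can keep an event that the site judged related and unexpected out of 15-day reporting to the main REC, without disclosure that opinions differed. This is a stated rule, so it is more than detail left for another document.

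The effect is confined to expedited safety oversight. The size in events is unknown: the protocol gives no count of related and unexpected SAEs and no rate of disagreement, and none should be invented. The primary endpoint of death, myocardial infarction or heart failure hospitalisation is collected from medical records and does not depend on this clause. The conclusion assumes that a downgraded event is treated as outside the category in section 12.2.3, which is the natural reading of a downgrade made before reporting. It is a cheap improvement.

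**What to change.** Reconcile section 12.2.3 with both lists of responsibilities in section 12.3. Suggested wording for the Chief Investigator's item:

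*An event that the site assesses as related and unexpected is reported to the Sponsor and the main REC within the times in section 12.2.3. If the Chief Investigator disagrees, that opinion and the reasons for it are attached to the report. The site's assessment is kept in the eCRF.*

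This keeps the Chief Investigator's review and lets the committee see both views. The cost is one or two sentences of protocol text, and possibly a few more expedited reports that the Chief Investigator considers unnecessary.

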#### RCB

1) Preparing annual safety data for inclusion in reports Trial Steering Committee (TSC).

2) Notifying Investigators of Related & Unexpected SAEs (by email) which compromise patient safety.

#### Trial steering committee (TSC)

In accordance with the Trial Terms of Reference the TSC will periodically review safety data and unblinded overall data to determine patterns and trends of events, or to identify safety or trial conduct issues, which would not be apparent on an individual case basis.

# **13. OUTCOME MEASURES**

#### **13.1 PRIMARY ENDPOINT**

Time to first composite endpoint measured from randomisation for a minimum of 12 months:

- All cause death
- myocardial infarction
- Heart failure hospitalisation

#### **13.2 SECONDARY ENDPOINTS**

- Total MACE events (MACE is defined as all-cause mortality, MI and heart failure hospitalisations)
- Total (first and recurrent) HF hospitalisations
- Total Cardiovascular (CV) death
- Total all-cause mortality
- KCCQ-CSS at 6 and 12 months
- EQ5D at 6 and 12 months

# **13.3 EXPLORATORY ANALYSES**

- Superiority of CTCA vs stress CMR (time to event analysis of primary endpoint)
- KCCQ-OSS at 6 and 12 months
- KCCQ-TSS at 6 and 12 months
- Myocardial infarction
- Procedural complications
- Time to diagnosis (which will be impacted by NHS waiting lists)

#### **14. SAMPLE SIZE**

We will aim to recruit both outpatients and inpatients who have suffered decompensated heart failure who have poor outcomes (annualised major adverse cardiovascular event rates of 15-46% in trials) . There are no prior trials of imaging strategy in heart failure on which to base a proposed non-inferiority margin. In MR-INFORM, a randomised trial of stress CMR vs ICA in patients with angina pectoris an absolute non-inferiority margin of 6% (equating to hazard ratio 1.6) was used. Non-inferiority hazard ratios vary in cardiovascular trials between 1.05 and 2.85 , and by selecting a non-inferiority margin at the very conservative end of this range we will maximise confidence in our findings.

The primary analysis will compare the two non-invasive strategies (combined) to the invasive strategy. Assuming 3.5 years recruitment, plus a year of follow-up (4.5 years maximum follow-up) and complete follow-up, there will be 90% power to demonstrate non-inferiority at a margin of HR=1.22 at 5% significance (i.e. one-sided p<0.025) with 982 per group (calculated using nQuery 9). Given the pragmatic study design and passive follow-up, we anticipate that withdrawals will be minimal and have therefore only increased the target by 2% (i.e. 3000 total, 1000 per arm).

The sample size calculation is based on recruitment over 3 years, with an additional year of follow-up (though we anticipate that recruitment will start slowly and increase, so we have allowed an additional 6 months to "ramp up"). To have 90% power to show non-inferiority (one-sided p=0.025), with a non-inferiority margin defined as a HR of 1.22 (which equates to a 6% absolute risk difference at 2 years), we require the observation of 1196 first events. Note, for a 1:1 randomisation this would be 1064 events, but in this study we are comparing the two non-invasive arms to the invasive arm as the primary analysis. The 2:1 randomisation implies that 1064 x 9  $\div$  8 events are required. Assuming recruitment at a constant rate over 3 years, plus an additional year of follow-up, this means recruitment of 982 per group (1964 non-invasive vs. 982 invasive).

To illustrate this further, 3 years of recruitment plus one year of follow-up implies an average of 2.5 years of follow-up per patient. An event rate of 35% over 2 years equates to 41.6 over 2.5 years (assuming exponential survival), so if we had a fixed follow-up of 2.5 years per patient, we would need to randomise a total of 1196  $\div$  0.416 = 2875 patients, or 959 per group, to observe 1196 events. This differs only slightly from the estimated 982 per group required when we have a variable follow-up time.

# **15. STATISTICAL ANALYSIS PLAN**

# **15.1 GENERAL CONSIDERATIONS**

Statistical analysis will follow a pre-determined plan . All analyses will be conducted on the Intention-totreat (ITT) population where a patient's diagnostic pathway will be that allocated at randomisation. A perprotocol population (PP) will also be defined for planned sensitivity analysis of the primary outcome and will include all participants according to the treatment randomised to, excluding participants who did not have sufficient exposure to their randomised investigation. This population will be defined in agreement with the external Trial Oversight Committee members.

# **15.2 FREQUENCY OF ANALYSIS**

Interim reports will be presented to the independent Trial Oversight Committee in strict confidence at annual meetings. No formal interim unblended analyses of the primary outcome are planned.

Final analysis of the primary outcome measure will be following a minimum 12-month follow-up of all patients. Analysis of long-term outcomes is planned based on electronic health records.

# **15.3 ANALYSES OF PRIMARY OUTCOME MEASURE**

Statistical analyses will follow a pre-determined statistical analysis plan, to be signed-off prior to any analyses being performed. All analyses will be conducted according to the intention-to-treat (ITT) principle, i.e. according to the diagnostic pathway allocated at randomisation. Initially, the two non-invasive pathways will each be compared for non-inferiority to the invasive standard of care. Subsequently the two non-invasive pathways will be compared for superiority against each other. All participants will be included in the analysis, up to the time of first event or censoring (being alive and event free). Unadjusted Kaplan-Meier estimates of survivor functions will be presented graphically. Survival between groups will be compared by a log-rank test, stratified by LVEF, and Cox Proportional Hazards regression, adjusted for LVEF. Differences between pathways will be reported as hazard ratios with 95% confidence intervals. Similar principles will be followed for other outcomes, using appropriate types of regression models. Missing data will not be imputed in main analyses, but multiple imputation methods may be applied in sensitivity analyses.

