#### TSC Trial steering committee

# **4.2 STUDY DEFINITIONS**

Heart Failure Classification (New York Heart Association Functional Classification)

- **Class I:** No Limitation of physical activity. Ordinary physical activity does not cause undue fatigue, palpitation or dyspnoea
- **Class II:** Slight limitation of physical activity. Comfortable at rest, but ordinary physical activity results in fatigue, palpitation or dyspnoea.
- **Class III:** Marked limitation of physical activity. Comfortable at rest, but less than ordinary activity causes fatigue, palpitation or dyspnoea.
- **Class IV:** Unable to carry out any physical activity without discomfort. Symptoms of cardiac insufficiency may be present, even at rest. If any physical activity is undertaken, discomfort is increased.

Heart Failure according to Left Ventricular Ejection Fraction

- Heart failure with reduced ejection fraction (HFrEF) defined as left ventricular ejection fraction (LVEF)≤40%.
- Heart failure with preserved ejection fraction (HFpEF) defined as LVEF>40%.
- Where image quality on initial echocardiogram prohibits assessment of LVEF by Simpson's biplane those with severe, moderate-severe and moderate left ventricular systolic dysfunction will be classified as HFrEF. Those with normal, mild or mild-moderate left ventricular systolic dysfunction will be classified as HFpEF.

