#### 9.3 RANDOMISATION

Randomisation to one of the three trial arms will be performed centrally using the RCB automated web randomisation system. Imaging assignment will be stratified by centre and ratio of HFpEF:HFrEF using randomly permuted blocks of varying size, with 1:1:1 allocation between the CTCA, stress CMR and invasive coronary angiography arms.

Study participants will be informed that they are free to withdraw consent for the study at any time.

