Where missing data are encountered, we will explore the assumptions regarding the missing data mechanism and decide upon an imputation method based on best practice. The mean total cost and mean total QALY gain per patient, according to randomisation group, will be estimated using a generalised linear model (GLM) and adjusting for trial minimisation factors and potential confounding factors. The appropriate family for the GLM will be selected based on the results of the modified Park's test. Cost-effectiveness at 12 months will be expressed as the incremental cost-effectiveness ratio (ICER) and net monetary benefit (NMB). We will assume a willingness-to-pay for QALY gains of £20,000. We will undertake probabilistic sensitivity analysis, using non-parametric bootstrapping, to explore the uncertainty in our results and plot the probability of cost-effectiveness on the cost-effectiveness acceptability curve. We will also undertake sensitivity analysis, using conceptual model-mediated regression analyses to explore the drivers – inputs

(imaging strategy), mediators (e.g. hospitalisations, procedural complications, time to diagnosis) of outcomes (costs and QALYs).

For the lifetime horizon, a health economic model will be developed. This will be informed by the existing literature. An initial scoping review did not identify any lifetime cost-effectiveness analyses of non-invasive imaging, compared with invasive coronary angiography, in patients with heart failure. However, there is clear evidence from patients with suspected angina that the choice of first-line test can influence downstream management and healthcare costs .

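### The primary log-rank and Cox models use only LVEF, although randomisation is stratified by centre and HFrEF/HFpEF class; Section 15.6 adjusts for minimisation factors that the trial does not have

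*Protocol*

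**What the plan says.** Three sections of the protocol name the factors to be balanced or adjusted for.

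- **Section 9.3 (Randomisation):** "Imaging assignment will be stratified by centre and ratio of HFpEF:HFrEF using randomly permuted blocks of varying size". The factors are centre and heart failure class, the method is blocking, and the three arms are of equal size.
- **Section 15.3 (Primary outcome):** "Survival between groups will be compared by a log-rank test, stratified by LVEF, and Cox Proportional Hazards regression, adjusted for LVEF". Centre does not appear. The same section extends the approach: "Similar principles will be followed for other outcomes, using appropriate types of regression models".
- **Section 15.6 (Costs and outcomes):** the cost and QALY models are to be fitted "adjusting for trial minimisation factors and potential confounding factors".

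Section 4.2 defines HFrEF as LVEF of 40% or less and HFpEF as LVEF above 40%. It adds a fallback for scans on which the biplane method cannot be used ("Where image quality on initial echocardiogram prohibits assessment of LVEF"): the class is then taken from the qualitative grade of left ventricular dysfunction.

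**The concern.** When allocation is balanced within strata, the usual expectation is that the analysis conditions on those strata, or that the plan says why not. Here the protocol names the adjustment set for the primary outcome and includes at most one of the two randomisation factors.

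**Centre.** The protocol gives reasons to expect centres to differ. Sites mix tertiary and district general hospitals (10.1), timing of the test after an acute admission is left to the site (9, 10.1), tests are performed and reported locally as in usual care (10.2), and time to diagnosis will depend on waiting lists (13.3). If centres differ in event rate and the Cox model ignores them, the estimated hazard ratio is pulled towards 1 relative to the within-centre value. In a non-inferiority comparison that direction favours the claim.

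**LVEF.** A stratified log-rank test needs categories, while a Cox covariate could be continuous. The wording allows the test and the hazard ratio to rest on different variables.

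**Minimisation factors.** None exist in this trial, so part of the covariate set in Section 15.6 cannot be identified from the protocol.

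**Working it through.** **1. Sections side by side**

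| Section | Centre | HFrEF/HFpEF class | Method or model |
|---|---|---|---|
| 9.3 | yes | yes | permuted blocks |
| 15.3 | not named | LVEF, form not stated | stratified log-rank, Cox |
| 15.6 | not named | not named | GLM, minimisation factors |

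**2. The protocol's own figures**

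Inputs from Section 14: margin HR 1.22, one-sided 0.025, power 90%, pooled non-invasive arms against invasive (2:1), 3 years of uniform accrual plus 1 year. The event rate of 35% at 2 years comes from the illustration that follows.

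- Events, 2:1: (1.960 + 1.282)² / [(ln 1.22)² × 2/9] = 1196. Stated: 1196.
- Events, 1:1: the same with 1/4 in place of 2/9 gives 1063. Stated: 1064.
- Hazard: λ = −ln(0.65)/2 = 0.2154 per year. Event probability = 1 − (e^(−λ) − e^(−4λ))/(3λ) = 0.4062. Then 1196/0.4062 = 2945, or 982 per group. Stated: 982.

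The calculation has no centre term, so none of these figures depends on how centre is handled.

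**3. Effect of ignoring centre**

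The documents give no between-centre variance, so a range is assumed for the SD of the log hazard. Simulation: 20 centres (the stated minimum), 2946 patients, blocks of three within centre and class, the hazard and accrual above, and log-normal centre effects. Half the patients are assumed HFpEF, with an assumed log hazard difference of 0.4 between classes. The true within-centre HR is 1.22, with 3000 trials per row (Monte Carlo error about 0.3 percentage points). The third column shows the spread of centre hazards that each SD implies, exp(2 × 1.96 × SD).

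| Analysis strata | SD | 95% fold range of hazards | Mean HR | One-sided error |
|---|---|---|---|---|
| class only | 0 | 1.0 | 1.220 | 2.1% |
| centre × class | 0 | 1.0 | 1.220 | 2.1% |
| class only | 0.2 | 2.2 | 1.217 | 2.6% |
| centre × class | 0.2 | 2.2 | 1.219 | 2.6% |
| class only | 0.4 | 4.8 | 1.207 | 3.5% |
| centre × class | 0.4 | 4.8 | 1.218 | 2.6% |
| class only | 0.6 | 10.5 | 1.197 | 4.3% |
| centre × class | 0.6 | 10.5 | 1.220 | 2.8% |

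A separate simulation at intermediate values gave 3.2% (class only) against 2.9% (with centre) at SD 0.3, and 3.9% against 2.7% at SD 0.5.

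A rough formula agrees. The standard error of the log HR is 1/√(1196 × 2/9) = 0.0613, and error ≈ Φ(−1.96 + (0.1989 − log HR)/0.0613), where 0.1989 = ln 1.22. With a large-sample unadjusted log HR of 0.195 at SD 0.3, this gives about 2.9%. With 0.186 at SD 0.5, it gives about 4%.

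**4. Precision and power**

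In the same simulation the standard error of the log HR is about 0.06 under both analyses. Power at a true HR of 1.0 is about 0.89 to 0.93 under both. With 20 centres and two classes there are 40 strata, so 1196/40 ≈ 30 events per stratum on average.

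**5. Which margin?**

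Section 14 also expresses the margin as a 6% absolute difference at 2 years. From 35%, (1 − 0.65^1.22) − 0.35 = 0.4088 − 0.35 = 5.88 points. With overall invasive-arm risk held at 35%, a within-centre HR of 1.22 corresponds to 5.75 points at SD 0.3 and 5.52 points at SD 0.5, both short of 5.88. With the truth set at 5.88 points, the Cox model that ignores centre has a one-sided error of about 2.1% at both SDs. The inflation in step 3 therefore appears only when 1.22 is a within-centre ratio.

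**The case against.** **The LVEF wording has a natural reading.** A log-rank test is stratified by categories, and the only LVEF categories the protocol defines are HFrEF and HFpEF. This stands: the factor is ambiguous rather than omitted. A reader might infer that patients without a numeric LVEF would be dropped, since Section 15.3 does not impute in main analyses, and that intention-to-treat is thereby broken. The documents do not support that as a definite finding. Section 15.3 says all participants are included, and Section 4.2 supplies a class where biplane assessment fails without saying that such patients have no LVEF value at all. It remains a risk only if the Cox covariate is numeric.

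**The error inflation depends on the estimand.** The protocol does not say that 1.22 is a within-centre ratio, and against the overall risk difference there is no inflation (step 5). This stands. The between-centre SDs are also assumed, and 0.5 implies a sevenfold range of hazards across centres.

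**Centre handling belongs in the statistical analysis plan.** Section 15.3 defers to a plan signed off before any analysis. Pooling rules and the choice between strata and frailty can indeed be left there. But the protocol does not leave the adjustment set open: it states one, and centre is not in it. A later plan that adds centre would depart from the stated model without explanation.

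**Conclusion.** The mismatch is real and can be read directly from Sections 9.3, 15.3 and 15.6. The primary models omit centre without a reason, the form of LVEF is not fixed, and the economic models refer to a randomisation method that is not used.

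The statistical consequence is modest and conditional. If 1.22 is a within-centre hazard ratio and the between-centre SD of log hazard is 0.3 to 0.5 (assumed), one-sided error is about 3 to 4% when centre is ignored. At 0.2 or below the effect is negligible. If the margin is the overall 2-year risk difference, no inflation was found.

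A reader might also infer that leaving centre out discards precision. The check does not support this: standard error and power are essentially the same either way, and the sample size is unaffected. The case for change is an analysis that matches the design, with some protection if centres differ substantially. Grade: minor.

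**What to change.** - **Section 15.3:** state that the log-rank test and Cox model are stratified by HFrEF/HFpEF class as randomised and by centre, with small centres pooled by a pre-stated rule, or with a centre frailty term in the Cox model. The class must be known at randomisation, so using it removes any question of missing LVEF values.
- **Other outcomes:** say that the same factors are carried into those models.
- **Section 15.6:** replace minimisation factors with randomisation stratification factors.

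The cost is wording only. Patients, data collection, event target and sample size do not change. Very small centres would lose a little information under full stratification, which pooling or the frailty term avoids.
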